11.10 Unscheduled visits

Unscheduled measurements will not be included in by-visit table summaries, but will contribute to the baseline value and best/ worst case value where required.

Descriptive statistics (mean, SD, median, minimum, maximum) by normal visit or time point for safety endpoints such as laboratory measurements, ECGs and vital signs will include only data from scheduled visits.

11.11 Conversion factors

The following conversion factors will be used to convert days into months or years:

1 month = 30.4375 days

1 year = 365.25 days.

11.12 Common calculations

For quantitative measurements, change from baseline will be calculated as:

Test Value at Visit X – Baseline Value

11.13 Handling of discontinued subjects.

Unless otherwise specified, data from discontinued subjects will not be replaced.

11.14 Handling of missing data

Handling of missing data for PK parameter calculations are discussed under Section [16.3.2](#).

In all subject data listings, imputed values will be presented. In all listings imputed information will be flagged.

Missing statistics, e.g., when they cannot be calculated, should be presented as “nd”. For example, if n=1, the measure of variability (SD) cannot be computed and should be presented as “nd”.

For the derivation of new date variable, the following rules will apply:

Partial birth dates will be handled this way: day will be imputed as 15 if it is missing, and month imputed as June if missing. If both of day and month are missing, they will be imputed as July 1st. If year is missing then the date will not be imputed.

In case the last administration date is incomplete the date of last administration will be taken from the Treatment Termination eCRF page.

Any adverse event (AE) with incomplete start/time and or end date will be handled as described below for the classification as treatment-emergent, assignment to treatment periods, and calculation of duration.

- AE with unknown start time but known start date, will be imputed with a time of 00:00 hours, unless the start date corresponds to any given dosing date, in which case time of dosing will be used instead. However, if this results in a start time after end time of the AE, then the start time will be imputed to 00:00 hours instead.
- Any AE with completely unknown start date will be imputed with date and time of the first IMP administration, unless the end date (imputed if needed) is known and prior to first IMP administration. In the latter case, the start date will be missing.
- AE with partially missing start date but in the same year (when day and month are missing) or in the same month and year (if the day is missing) as first IMP administration then the start date will be replaced by the minimum between first IMP administration and AE resolution date. In all other cases the missing onset day or onset month will be replaced by 01.
- Adverse event with completely unknown end date will be imputed with the date of study completion (or in case of withdrawal, date of discontinuation).

Partially known end dates will be treated as follows:

- If only the day is missing, the last day of the month will be imputed or the date of study completion/discontinuation if earlier.
- If day and month are both missing, then the end date of 31 December will be imputed or the date of study completion/discontinuation if earlier.

Assignment to the different treatment periods will be performed after the imputations have been performed. An AE will be assigned to a specific treatment period if it occurs on or after the IMP administration scheduled for that period and before the IMP administration in the next period (or study completion for the last period).

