8.3.2 Method of Detecting Adverse Events and Serious Adverse Events

At each study visit, the participant will be queried on changes in his/her condition. During the reporting period of the study any unfavorable changes in the participant's condition will be recorded as AEs, whether reported by the participant or observed by the Investigator.

All AEs must be documented in the appropriate section of the eCRF. Complete, accurate and consistent data on all AEs experienced for the duration of the reporting period (defined below) will be reported on an ongoing basis. Among these AEs, all serious AEs and non-serious adverse drug reactions (ADRs) must be additionally documented and reported using an SAE Report Form as described in [Appendix 4](#).

The following aspects must be recorded for each AE in the eCRF:

1. Description of the AE in medical terms, not as reported by the participant
2. Date/time of onset (only in relation to administration of IMP: before, during, or after)
3. Severity Grade assessed by the Investigator according to the Qualitative Toxicity Scale

4. Causal relationship to the IMP applied per protocol, assessed by the Investigator
5. Action taken with regard to study treatments
6. Concomitant medication
7. Outcome
8. Seriousness (appropriate criteria documented).

It is important that each AE report include a description of the event, its duration (onset and resolution dates (and times when it is important to assess the time of AE onset relative to the recorded treatment administration time), its severity, its causal relationship with the study treatment, any other potential causal factors, any treatment given or other action taken, and its outcome. In addition, serious cases should be identified and the appropriate seriousness criteria documented.

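### SAP 11.14 does not use the recorded before/during/after onset item when it imputes a missing adverse-event time on a dosing day, so a pre-dose event that persists to dosing or has no end time can be counted under the wrong period

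*SAP*

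**What the plan says.** SAP 11.14 sets the rules for incomplete AE times. The results are used "for the classification as treatment-emergent, assignment to treatment periods, and calculation of duration". When the start date is known and the time is not, the default is 00:00, "unless the start date corresponds to any given dosing date, in which case time of dosing will be used instead". The next sentence adds a fallback: "However, if this results in a start time after end time of the AE, then the start time will be imputed to 00:00 hours instead".

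The order of operations is explicit: "Assignment to the different treatment periods will be performed after the imputations have been performed". An AE then belongs to a period "if it occurs on or after the IMP administration scheduled for that period and before the IMP administration in the next period".

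Protocol 8.3.2 lists what must be recorded in the eCRF for each AE. The second item is "Date/time of onset (only in relation to administration of IMP: before, during, or after". The same section asks for onset and resolution dates, and for "times when it is important to assess the time of AE onset relative to the recorded treatment administration time".

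SAP 17.1 counts an AE as treatment-emergent if it starts after dosing in a period, or if it was already present and worsened after that dose. An AE that cannot be classified is treated as treatment-emergent. SAP 17.1.1 tabulates these events by treatment within the fasting and fed groups, as event counts and as number and percentage of subjects.

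**The concern.** The protocol makes clock times conditional but lists onset relative to dosing for every AE. An AE with a known position relative to the dose and no clock time is therefore a foreseeable record. For that record the SAP imputes a time without looking at the known position, and the imputed time then decides both treatment-emergent status and the product column.

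This matters most on Day 8. In a crossover, an event with onset just before the second dose falls in Period 1 by the SAP's own definition. Moving it to the dosing time moves it from one product to the other. Pre-dose onset on a dosing day is plausible: participants have fasted overnight (Protocol 6.8.3), first-day blood samples are drawn through an indwelling cannula with a baseline draw about 10 minutes before dosing (Protocol 8.5), and the fed group eats a high-fat breakfast in the preceding 30 minutes (Protocol 6.1.2). Comparing safety and tolerability is a secondary objective, and in a group of 16 a single event is visible in the tables.

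**Working it through.** The plan states no figure on this point, so the check is to apply the rules to each kind of event.

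**Inputs**
- Imputation rule, end-time fallback and period rule: SAP 11.14.
- Treatment-emergent definition: SAP 17.1.
- Onset item: Protocol 8.3.2.
- Group sizes of 38 (fasting) and 16 (fed), with dosing on Days 1 and 8: SAP 7.2.
- Dosing time: the protocol says only that it is in the morning. Take 08:00 as an assumption; any time after 00:00 gives the same pattern.

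**Rules in symbols.** Let D be the dosing time on that day, E the AE end time and S the imputed start.
- S = D, unless D > E, in which case S = 00:00.
- On Day 8, S ≥ D gives Period 2 and S < D gives Period 1.
- On Day 1, S ≥ D gives Period 1 and S < D gives pre-treatment.

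**Results.** The start time is missing throughout, and the event does not worsen after the dose.

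| Day | Event | By true onset | SAP rule | Onset item used first |
|---|---|---|---|---|
| 1 | Pre-dose, ended pre-dose, end time known | Pre-treatment | Pre-treatment | Pre-treatment |
| 1 | Pre-dose, ended after dose | Pre-treatment | **Period 1** | Pre-treatment |
| 1 | Pre-dose, end time unknown | Pre-treatment | **Period 1** | Pre-treatment |
| 1 | Post-dose | Period 1 | Period 1 | Period 1 |
| 8 | Pre-dose, ended pre-dose, end time known | Period 1 | Period 1 | Period 1 |
| 8 | Pre-dose, ended after dose | Period 1 | **Period 2** | Period 1 |
| 8 | Pre-dose, end time unknown | Period 1 | **Period 2** | Period 1 |
| 8 | Post-dose | Period 2 | Period 2 | Period 2 |

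Four of the eight cases are misplaced under the SAP rule, and none when the recorded item takes precedence. These are counts of constructed cases, not expected frequencies.

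Two details explain the bold rows. With no end time, the test D > E cannot be evaluated; if the end date is wholly unknown, SAP 11.14 imputes the date of study completion or discontinuation, so the fallback will normally not apply. On Day 1, SAP 17.1 says after the dose while the period rule says on or after. An imputed time exactly equal to the dose is thus borderline under SAP 17.1, but the period rule and the treatment-emergent default both push it into Period 1.

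**Size per event.** Moving one Day 8 event removes one participant from one product column and adds one to the other:
- Fasting: 1/38 = 2.6 points in each column, so the product difference shifts by 2/38 = 5.3 points.
- Fed: 1/16 = 6.3 points in each column, so the difference shifts by 2/16 = 12.5 points.

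A Day 1 event adds one false participant to one column: 2.6 or 6.3 points.

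**The case against.** A reader might infer that every AE with a missing time on a dosing day is misplaced. The documents do not support that. Post-dose events are placed correctly, and the fallback sentence correctly places a pre-dose event known to have ended before the dose. An event that worsened after the Day 8 dose counts as treatment-emergent in Period 2 under SAP 17.1 in any case.

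Other points against the concern carry weight:

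- **The eCRF is not in the documents.** The Protocol 8.3.2 item may describe a separate field, or may only say that timing is needed so far as it places onset relative to the dose. The AE listing contents in Protocol 9.4.4 and SAP 17.1 show no such field. Whether recorded data would actually be overridden therefore depends on a form that cannot be checked here.
- **The trigger is narrow.** Participants are inpatients from Day -1 to Day 10, AEs are recorded on both dosing days, and a dosing morning is just when Protocol 8.3.2 wants clock times. Missing times there may be rare.
- **Period 1 attribution is a convention.** A Day 8 pre-dose event begins seven days after the Period 1 dose and may be procedural. The period rule puts it under the Period 1 product; that does not make that product its cause.
- **Safeguards exist.** SAP 11.14 flags imputed values in listings, and the investigator's causality assessment is recorded separately.

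The remaining defence, that the rule is conservative, does not hold. The SAP 17.1 default is for events that cannot be classified, whereas a recorded onset item would allow classification. It also settles only whether an event is treatment-emergent; on Day 8 the question is which product is charged. Flagging in listings does not correct the table counts.

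**Conclusion.** The point stands in limited form. As written, SAP 11.14 places an AE recorded as starting before the Day 8 dose under the Period 2 product when three conditions hold: the clock time is missing, the event is still present at dosing or lacks an end time, and it did not worsen after the dose. The Day 1 equivalent becomes a false treatment-emergent event.

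The shifts of 5.3 points (fasting) and 12.5 points (fed) are maxima per Day 8 event. They assume that all 38 or 16 participants are dosed in both periods and that the participant has no other AE of the same term under either product. The documents give no basis for estimating how many such events would occur, so no overall effect can be stated. The consequence is confined to descriptive by-treatment safety tables. A reader should not infer any effect on the bioequivalence conclusion, which rests on AUC0-t and Cmax and does not use AE times. The severity is minor, and the change is an optional clarification.

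**What to change.** Amend the first AE bullet of SAP 11.14. When the start date is a dosing date and the start time is missing, use the recorded relative-onset item first:
- *before*: impute 00:00, which gives pre-treatment on Day 1 and Period 1 on Day 8;
- *during* or *after*: impute the dosing time.

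Keep the present rule, including its end-time fallback, only where the item is missing or was not captured in the eCRF. State that the exacerbation rule in SAP 17.1 still applies, so an event that worsens after a dose remains treatment-emergent in that period.

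The cost is one SAP sentence and one line of derivation code, with no new data if the eCRF holds the item as Protocol 8.3.2 describes. One side effect is that imputing 00:00 can lengthen the calculated duration by up to the hours between midnight and the dose; the SAP already accepts this on non-dosing dates.

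### Incomplete AE start dates default to the Period 1 dose, so most Period 2 AEs with such dates are tabulated under the Period 1 product

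*SAP*

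**What the plan says.** SAP 11.14 states that its rules for incomplete AE dates serve "classification as treatment-emergent, assignment to treatment periods, and calculation of duration". Four rules bear on the start date:

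- Only the time missing: midnight, "unless the start date corresponds to any given dosing date, in which case time of dosing will be used instead".
- Day missing: "the start date will be replaced by the minimum between first IMP administration and AE resolution date". This holds only for a partial date that shares the first dose's month and year. If the month is missing too, sharing the year is enough.
- Any other partial date: "In all other cases the missing onset day or onset month will be replaced by 01".
- No date at all: "Any AE with completely unknown start date will be imputed with date and time of the first IMP administration". The only exception is an AE that ended before that dose.

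The order is explicit: "Assignment to the different treatment periods will be performed after the imputations have been performed". An AE belongs to a period if it occurs "on or after the IMP administration scheduled for that period and before the IMP administration in the next period". SAP 11.15 ties the first administration to Period 1 (Trial Day 1), SAP 7.2 gives the other product on Day 8, and SAP 17.1.1 tabulates treatment-emergent AEs (TEAEs) by treatment within each food group.

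**The concern.** In a parallel trial, defaulting an uncertain onset to the first dose is cautious: it leans towards calling the event treatment-emergent and cannot change the treatment it is counted under. In this crossover the imputed date also selects the product. The date rules know only the Period 1 dose. The resolution date can pull a start earlier but never later, so an AE that resolved on Day 9 gives no protection against a Day 1 imputation.

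Comparing the safety of the two products is a secondary objective, and the groups are small. If everyone is dosed in both periods, moving one participant's only event from one product to the other lowers one incidence and raises the other. The difference then shifts by 2/16 = 12.5 percentage points in the fed group and 2/38 = 5.3 points in the fasting group.

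**Working it through.** The plan gives no figure on this point, so there is none to reproduce.

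**Inputs.** The imputation and period rules of SAP 11.14, and Day 8 = Day 1 + 7 days (SAP 7.2). Assumptions: Day 1 is equally likely on each date of a 365-day year, and the resolution date is known and one day after onset.

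**Single case.** Day 1 is 10 July. An AE starts on 18 July (Day 9), is recorded only as July, and resolves on 19 July. The imputed start is min(10 July, 19 July) = 10 July, which precedes the Day 8 dose of 17 July. The AE is assigned to Period 1 and the other product.

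**Day missing, true onset on Day 8, 9 or 10.** There are 365 × 3 = 1095 combinations. Take a month of L days with Day 1 on date d, so that onset falls on d + 7, d + 8 or d + 9.

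- Same month as Day 1: (L − 7) + (L − 8) + (L − 9) = 3L − 24 combinations. Over the year this is 3 × 365 − 12 × 24 = 807. All 807 are imputed to the Day 1 dose, hence Period 1.
- Next month: 7 + 8 + 9 = 24 per month, or 288 a year, imputed to the 1st. The event stays in Period 2 only if the Day 8 dose is on or before that 1st, that is d ≤ L − 6. This leaves 1 + 2 + 3 = 6 per month, or 72 a year. The other 288 − 72 = 216 go to Period 1.
- Total to Period 1: 807 + 216 = 1023, and 1023/1095 = 93.4%.

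**Other patterns**, by the same enumeration:

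| Missing part | True onset | Assigned to Period 1 |
|---|---|---|
| Day | Day 8–15 | (1912 + 576)/2920 = 85.2% |
| Day and month | Day 8–10 | (807 + 282)/1095 = 99.5% |
| Whole date | Day 8–10 | 100% |
| Time only, on Day 8 | Day 8 | 0% (set to the Day 8 dosing time) |

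No Period 1 event (onset Day 1–7) moves to Period 2, so the error runs from Period 2 to Period 1 only.

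**Effect on the tables.** Let q be the share of all Period 2 AEs that is moved, with 1:1 sequences and no period effect. Half of each product's administrations fall in Period 2, so the observed rates are

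- test: pT − (q/2)(pT − pR)
- reference: pR + (q/2)(pT − pR)

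and the observed difference is (1 − q)(pT − pR). With illustrative rates pT = 0.20 and pR = 0.10, q = 10% gives 0.195 and 0.105, a difference of 0.09 instead of 0.10. For assumed q of 5%, 10% and 20% the retained fraction is 0.95, 0.90 and 0.80.

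**The case against.** The strongest reply is that the rule will seldom be used. Participants are inpatients from Day −1 to Day 10 (Protocol Table 1, note a), and AEs are recorded at each visit for the time since the previous one (note i). Onset is to be documented relative to dosing (Protocol 8.3.2), and analysis waits until queries are resolved (SAP section 8). That stands, and it is why the point is minor.

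It is also said that flagging imputed values in the listings exposes any error. This stands in part: a flag does not correct a summary table, and the documents do not say whether the listed treatment at onset is collected or derived from the imputed date.

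SAP 17.1 defines treatment-emergence by the first administration of each period, so one could read 11.14 the same way. But 11.14 omits that qualifier and 11.15 ties the term to Period 1. Where 11.14 means either dose, in the missing-time rule, it says so.

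A reader might infer more than the documents support:

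- **That every incomplete date goes to Day 1.** Missing times are handled correctly, partial dates outside the first dose's month follow the 01 rule, and 72 of the 288 different-month cases stay in Period 2. A missing end date alone does not move the period.
- **That 93.4% is a rate of misattributed AEs.** It is conditional on the day already being missing. The documents give no rate of incomplete dates.
- **That the by-product safety comparison is defeated, or tilted to one product.** Any contrast among the moved events is lost, but the table as a whole is diluted only by q, and balanced sequences favour neither product in expectation.

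**Conclusion.** The rule is wrong as written for one of its own stated purposes, period assignment. Given an incomplete start date (day, month or whole date), most Period 2 AEs are charged to the Period 1 product: 100% in the first dose's month, and about 93% of Day 8–10 onsets with a missing day. The latter figure rests on equally likely Day 1 dates and a known resolution date.

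The consequence is dilution of descriptive by-treatment TEAE tables by a factor (1 − q). This rests on 1:1 sequences and no period effect; q is unknown and expected to be small. The AUC and Cmax bioequivalence decision and the overall TEAE counts do not depend on the rule. Minor severity.

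**What to change.** Amend SAP 11.14 for AE starts with a missing day, month or whole date:

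1. Bound the onset by the visit at which the AE was first recorded (it began since the previous visit), the known date parts and the resolution date.
2. If only one period is compatible, impute to that period's IMP administration.
3. If both remain compatible, default to neither dose. Count the AE under both treatments in the by-treatment TEAE tables and once in the overall counts, and flag it. State what is then used for duration, which 11.14 also derives from the imputed start.

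The missing-time rule and the exception for AEs that ended before the first dose can stay.

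A simpler repair, imputing to the latest dose compatible with the date parts and the resolution date, should not be used alone. It removes the Period 2 error but creates the reverse one. Of the 365 × 7 = 2555 Period 1 onsets with a missing day, none moves to Period 2 if resolved the same day. If resolved one day later, 353 move (365 − 12; 13.8%). If resolved three days later, 1023 move (329 + 341 + 353; 40.0%). The visit bound is what limits this.

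The cost is a few lines of SAP text and a small change to the ADaM derivation. The downside is that a few events may appear under both products.

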9.4.4 Analysis of Safety and Other Endpoints

All data recorded during the study will be presented in individual data listings performed on the Safety Population.

All safety variables will be analyzed using descriptive statistics.

For the evaluation of safety parameters, the continuous variables will be summarized descriptively per treatment, period, time point, and overall by N, arithmetic mean, median, standard deviation (SD), standard error of the mean (SEM), and minimum and maximum values. Categorical variables will be presented in frequency tables with the counts of observations and corresponding percentages.

Vital sign measurements and ECG recordings will be individually listed by treatment, participant number, period, and time point, and the abnormal values flagged according to reference laboratory ranges. All hematology and biochemistry parameters will be listed and summarized using descriptive statistics by treatment sequence on observed values. Urinalysis will be summarized in frequency tables.

After coding of AEs according to the Medical Dictionary for Regulatory Activity classification (current version) and assignment to a system organ class and preferred term, all AEs recorded during the course of the study will be listed by treatment and participant number.

The AE listings will include the following items:

- System organ class
- Preferred term
- Investigator's description
- Whether the event is treatment-emergent
- Study treatment at onset of event
- Date and time of onset and resolution
- Duration of the event
- Date and time of last administration before AE
- Intensity
- Causality relationship to investigational product
- Outcome
- Action taken to investigational product
- Other action
- Seriousness.

Incidence of treatment-emergent adverse events (TEAEs) will be summarized using frequency of events and number of participants experiencing these events per treatment, preferred term, and system/organ class.

In addition, all TEAEs will be tabulated by intensity and relationship to drug per treatment and group. An AE will be considered “treatment-emergent” if it occurred after the first investigational product administration or if it occurred before the first investigational product administration and worsened after.

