17.1 Adverse Events

AEs will be coded using the MedDRA Version 21.0 or higher.

An AE will be considered as 'treatment emergent' if it occurred after the first IMP administration of each period or if it was present prior to first IMP administration but exacerbated after the first IMP administration of each period. All other adverse events will be considered 'pre-treatment'.

In the case where it is not possible to define an AE as TEAE or not, the AE will be classified as TEAE as the most conservative approach.

The AE listings will include the following items:

- System organ class
- Preferred term
- Investigator's description
- Whether the event is treatment-emergent
- Trial treatment at onset of event
- Date and time of onset and resolution
- Duration of the event
- Date and time of last administration before AE
- Study Day
- Severity
- Causality relationship to investigational product
- Outcome
- Action taken to investigational product
- Other action

- Seriousness

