17.1.1 All Adverse Events

A summary table describing all the TEAEs occurring during the trial will be produced overall and by group as well as by treatment for each group using frequency of events and number and percentage of subjects experiencing these events overall and by SOC and PT.

Group/SOC terms will be sorted by decreasing total frequency. Preferred terms (PT) within each group/SOC term will likewise be sorted by decreasing total frequency.

In addition, all TEAEs will be tabulated by severity and relationship to IMP in the same manner.

The relationship to the trial treatment, as indicated by the investigator, is classified as ‘unrelated’ or ‘related’. TEAE with a related or missing relationship to the trial treatment will be regarded as ‘related’.

Multiple occurrences of the same TEAE in one subject during the same treatment in the trial will be counted as multiple events in the frequency counts for adverse events. If a subject experiences more than one occurrence of the same AE during the same treatment in the trial, the subject will only be counted once for that treatment using the worst severity and the strongest relationship. The AE will be categorized as ‘unrelated’ only when all relationship records are ‘unrelated’, otherwise it will be classed as ‘related’ in the corresponding relationship summaries.

In case a subject had events with missing and non-missing severities, the maximum of the non-missing severities will be displayed. In case all the TEAEs of a subject are all with missing severities then Moderate will be used unless there is any evidence that it should be Severe.

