17.2 Deaths, Other Serious Adverse Events, and Other Significant Adverse Events

17.2.1 Deaths

AEs leading to Death are those events which are recorded as “Fatal” to the item “Change in severity and outcome” on the “Adverse Events Details” page of the eCRF. AEs leading to deaths will be listed by group, treatment sequence and subject including SOC, PT and investigators’ verbatim, if applicable.

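### The SAP ties an adverse event to a treatment period by onset only, so an event that becomes treatment-emergent by worsening can lack a product in the by-treatment tables

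*SAP*

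**What the plan says.** **Period assignment.** SAP 11.14 states: "An AE will be assigned to a specific treatment period if it occurs on or after the IMP administration scheduled for that period". The window closes at the next period's dose, or at study completion for the last period. The step comes after date imputation: "Assignment to the different treatment periods will be performed after the imputations have been performed". The rule sits under the missing-data heading but is worded for AEs in general, and neither document gives another.

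**Treatment emergence.** SAP 17.1 gives two routes. The first is onset after a period's dose. The second applies "if it was present prior to first IMP administration but exacerbated after the first IMP administration of each period". Protocol 9.4.4 has the same second route but ties it to the first dose of the study: an AE also counts "if it occurred before the first investigational product administration and worsened after".

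**Tabulation.** SAP 17.1.1 reports TEAEs "overall and by group as well as by treatment for each group", and treats severity and relationship likewise. When a participant has the same AE more than once under one treatment, "the subject will only be counted once for that treatment using the worst severity and the strongest relationship".

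**Recording.** The AE listing in SAP 17.1 carries "Trial treatment at onset of event" and has no item for the treatment at worsening. SAP 17.2.1 mentions an eCRF item labelled "Change in severity and outcome".

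**The concern.** Two rules have to work together and do not. SAP 17.1 decides whether an AE is treatment-emergent, and counts worsening. SAP 11.14 decides which product the AE belongs to, and looks only at onset. An AE that qualifies by worsening can therefore pass the first rule and have nowhere to go under the second.

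A secondary objective is to examine safety and tolerability after the test and the reference product, and the by-treatment TEAE table is the main output for it. AEs are collected from informed consent (protocol Table 1, footnote i, and 8.3.1), so AEs present before the first dose can exist. Without a stated rule, the product for such an event would be chosen during programming, in an open-label study where the treatment is visible.

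**Working it through.** There is no plan figure to reproduce. The check crosses every onset window with every worsening window and compares the two rules.

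**Inputs**
- One dose per period (protocol 2.3), so the first administration of a period is its only dose.
- Windows: 0 = before the Period 1 dose; 1 = from the Period 1 dose to the Period 2 dose; 2 = from the Period 2 dose to study completion.
- SAP 11.14: period = onset window if that is 1 or 2, otherwise none.
- SAP 17.1, each-period reading: treatment-emergent in the onset window if that is 1 or 2, and also in any later window in which the AE worsens.
- Narrow reading (protocol 9.4.4, and possible for SAP 17.1): worsening counts only for AEs present before the first dose of the study.
- Working assumption: a worsening stays on the original AE record, with at most one worsening per AE.

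*Occurs* in SAP 11.14 is read as onset for three reasons: SAP 17.1 itself contrasts occurring with being present and exacerbating, assignment follows imputation of start dates, and the listing shows treatment at onset.

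**Result.** Each sequence has 4 + 3 + 2 = 9 possible combinations (onset in window 0, 1 and 2 respectively).

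| Onset | Worsens | Emergent in, each-period reading | Emergent in, narrow reading | Period under 11.14 | Consistent? |
|---|---|---|---|---|---|
| 0 | never, or in 0 | none | none | none | yes (2 combinations) |
| 0 | 1 | Period 1 | Period 1 | none | no, on either reading |
| 0 | 2 | Period 2 | Period 2 | none | no, on either reading |
| 1 | never, or in 1 | Period 1 | Period 1 | Period 1 | yes (2 combinations) |
| 1 | 2 | Periods 1 and 2 | Period 1 | Period 1 | no on each-period, yes on narrow |
| 2 | never, or in 2 | Period 2 | Period 2 | Period 2 | yes (2 combinations) |

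So 3 of 9 combinations mismatch on the each-period reading and 2 of 9 on the narrow reading. The result is the same in both sequences. The mismatches are exactly the combinations in which worsening is what makes the AE emergent in that period. The counts describe logical cases, not how often they would happen.

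**What happens in the tables**
- Onset before Day 1: the event has no treatment column in the TEAE, severity and relationship tables. It remains in the overall and food-group totals and in the listings.
- Onset in Period 1, worse after Day 8 (each-period reading): the Period 1 count is right for the onset. The worsening is not counted under the Period 2 product, and the worst severity can be charged to the Period 1 product.

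**Size of one participant**, if everyone randomized receives both products (SAP 7.2, Table 5):
- fed group: 1/16 = 6.25%, about 6.3 percentage points;
- fasting group: 1/38 = 2.63%, about 2.6 percentage points.

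**The case against.** The strongest reply is that worsening may never sit on the original record. Protocol 8.3.2 has unfavorable changes in a participant's condition recorded as AEs. If a worsening is entered as a new AE, it has its own start date and SAP 11.14 places it correctly. This cannot be ruled out. Against it, the exacerbation clause in SAP 17.1 would then be largely redundant, and the eCRF label in SAP 17.2.1 hints at severity changes within one record. The documents leave the matter open.

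Two provisions might seem to close the gap but do not. The default in SAP 17.1 for unclear cases decides whether an AE is a TEAE, not which product it belongs to. The reference in SAP 11.2 to the most recent treatment governs the sorting of listings, not the AE tables.

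Three stronger readings are tempting and are not supported:
- *The event is charged to the wrong product.* An AE that began after the Period 1 dose belongs under the Period 1 product for its onset. What is missing is the later worsening, and only on the each-period reading. Protocol 9.4.4 points to the narrow one, and SAP section 9 declares no change from the protocol.
- *The eCRF already holds the date of the severity change.* SAP 17.2.1 gives only an item label, used there to find fatal outcomes. The list of items to record in protocol 8.3.2 includes no such date.
- *One participant could be 1/12 in the fed group.* Twelve is the replacement threshold and the number of evaluable participants. AE tables use the Safety Population, meaning everyone dosed at least once, so falling to 12 evaluable participants does not make the denominator 12.

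**Conclusion.** The gap is real and minor. If a worsening stays on its AE record, an AE that began before Day 1 and worsens after a dose is a TEAE with no product. That holds on either reading of SAP 17.1 and under protocol 9.4.4. The Period 1 to Period 2 case adds an uncounted worsening and a possibly misplaced severity, but only on the each-period reading.

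The effect is confined to the by-treatment columns, at one participant's share per event. Such events should be few in healthy volunteers given a single dose per period. Safety is a secondary, descriptive objective, and the bioequivalence conclusion does not depend on it. The point is still worth settling before database lock, because applying both rules as written drops the event from the tables that compare the products.

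**What to change.** 1. Add to SAP 11.14 and 17.1: a TEAE that qualifies by worsening is assigned to the period and product of the most recent dose before the worsening, with the severity reached in that period. Where the AE began in Period 1, its onset stays under the Period 1 product. The AE is counted once in overall totals.
2. Align the worsening clause of SAP 17.1 (each period) with protocol 9.4.4 (first administration). If the each-period form is kept, declare the difference in SAP section 9.
3. Confirm whether the eCRF captures the date of a severity change. If it does not, state that a worsening after a dose is entered as a new AE record with its own start date; SAP 11.14 then assigns it correctly.

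The cost is SAP wording, one derivation in the AE dataset and possibly one eCRF recording instruction. No participants or study procedures are added.
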